3 STUDY OBJECTIVES

3.1 Primary Objective

• To assess the efficacy of B244 in the treatment of pruritus in adults with a history of atopic dermatitis.

3.2 Secondary Objectives

• To assess the safety and tolerability of B244 in adults with a history of atopic dermatitis.

4 ENDPOINTS

4.1 Efficacy

4.1.1 Primary

• Mean change in WI-NRS from baseline to Week 4

4.1.2 Secondary

- Proportion of patients with ≥4 point improvement in WI-NRS from baseline to Week 4
- Proportion of subjects with any improvement in WI-NRS from baseline to Week 4
- Mean change in AI-NRS from baseline to Week 4
- Proportion of subjects with ≥ 4 point improvement in AI-NRS from baseline to Week 4
- Proportion of subjects with any improvement in AI-NRS from baseline to Week 4
- Mean change in WI-NRS from baseline to Week 2
- Proportion of subjects with ≥4 point improvement in WI-NRS from baseline to Week 2
- Mean change in POEM from baseline to Week 4
- Mean change in 5-D Pruritus Scale from baseline to Week 4

4.1.3 Exploratory

- Mean change in IGA from baseline to Week 4
- Mean change in EASI from baseline to Week 4

4.2 Safety & Tolerability

Safety and tolerability endpoints include the following:

- Incidence of TEAEs and SAEs
- Changes in vital signs and clinical laboratory parameters following study drug exposure
- Changes in local skin tolerability following application of study drug

5 STUDY DESIGN

- This is a Prospective, Vehicle Controlled, Double-Blind, Multicenter, Randomized Phase II Trial, comparing the effect of twice daily B244 applications for 4 weeks vs vehicle applications on treatment of mild to moderate pruritus associated with atopic dermatitis.
- Approximately 576 subjects may be enrolled.
- The total duration of the study will be approximately 11 weeks. Participants will report for a Screening visit and if all inclusion/exclusion criteria are met, subjects will go through a two-week washout phase (see Section 10.6.2) before reporting for a Baseline visit.
- After screening and baseline, participants will be randomized to one of two doses of B244 or vehicle application for 4 weeks.
- Randomization will be 1:1:1 so that an equal number of patients will be treated in each Arm of the study.
- All B244 randomized subjects will be treated at the dose of $1x10^{10}$ cells/ml (O.D. 5.0) or $4x10^{10}$ cells/ml (O.D. 20.0).
- Subjects must be willing and able to complete diary within a consistent time frame on a daily basis and to comply with restrictions on allowable therapies for the duration of the study.
- All subjects will attend a screening visit not more than 21 days prior to Baseline (Day 0). Subjects will be required to return to the clinic at Baseline, Day 14 (Week 2) and Day 28 (Week 4) visits. All subjects will be asked to attend a Week 8 follow-up visit 4 weeks (28 (±3) days) after the last dose of study medication.
- Subjects will apply a total of 10 pumps of IP per application across all affected areas twice-a-day (i.e. 10 pumps in the morning and 10 pumps again at night) for 4 weeks.
- Safety evaluations will consist of review of participant's medical history at screening and on-going assessment of adverse events reported throughout the study duration.

6 SELECTION OF STUDY PARTICIPANTS

6.1 Number of Participants Planned

Approximately 576 subjects (192 per treatment group) with pruritus and a history of atopic dermatitis will be randomized into this study.

6.2 Inclusion Criteria

Deviations from inclusion criteria are not allowed because they can potentially jeopardize the scientific integrity of the study, regulatory acceptability or participant safety. Therefore, adherence to the criteria as specified in the protocol is essential.

Participants eligible for enrollment in the study must meet all the following criteria:

- 1. Male and female subjects 18 to 65 years of age.
- 2. Pruritus of at least 4 weeks duration prior to the initial Screening visit and during the 2 week washout period.
 - a. Subjects using stable doses of oral H1 antihistamines at the initial Screening visit must be willing to continue these at the same doses and frequencies throughout the study inclusive of the follow-up period.
- 3. Worst Itch Numeric Rating Scale (WI-NRS) score ≥ 7 in the 24-hour period prior to the initial Screening as well as Baseline visits.
- 4. Average weekly WI-NRS score ≥6 for each week of the washout period, as recorded in the eDiary.
- 5. A history of atopic dermatitis for greater than 12 months consistent with a diagnosis of atopic dermatitis, as defined by the 2014 American Academy of Dermatology (AAD) Guidelines of Care for the Management of Atopic Dermatitis¹.
 - a. Subjects using bland emollients at the initial Screening visit will be allowed to continue to use their emollient of choice at a similar dose and frequency throughout the study, if used.
 - b. Subjects using low- to mid-potency topical corticosteroids at the initial Screening visit will be allowed to use their topical corticosteroid of choice at the same dose and frequency no more than 7 days per month throughout the study as rescue medication.
- 6. A minimum of 10% and not more than 40% of the subjects' BSA affected by atopic dermatitis (*affected* is defined by physical examination findings: erythema, edema, scaling, lichenification, excoriation, with the excoriation serving as the physical examination correlate of pruritus) at Screening and Baseline.
 - a. Subjects' BSA can include face and body OR body alone BUT NOT face alone.
- 7. An Investigator Global Assessment (IGA) score of 2-3 at Screening and Baseline.
- 8. Willing and able to complete once-daily eDiary entries within a consistent timeframe for the duration of the study and have ≥80% eDiary compliance rate during the washout period.
- 9. Judged to be in good health in the investigator's opinion.

6.3 Exclusion Criteria

Deviations from exclusion criteria are not allowed because they can potentially jeopardize the scientific integrity of the study, regulatory acceptability or participant safety. Therefore, adherence to the criteria as specified in the protocol is essential.

Participants will be excluded from the study if any of the following criteria are met:

- 1. Clearly defined etiology for pruritus other than atopic dermatitis. These include but are not limited to urticaria, psoriasis or other non-atopic dermatologic conditions, hepatic or renal disease, psychogenic pruritus, drug reaction, untreated hyperthyroidism, parasite presence and presence of acute infection either systemically or in the AD lesions.
- 2. Presence of any acute condition which may risk inducing an atopic dermatitis flare during the course of the study, such as impetigo or active herpes simplex infection.
- 3. Treatment with systemic corticosteroids within 4 weeks prior to randomization.
- 4. Treatment with Class III or higher potency topical corticosteroids or any topical antipruritic therapies (other than stable doses of low- or mid-potency topical corticosteroids or bland emollients) within 4 weeks prior to randomization.
- 5. Treatment with systemic therapies with recognized anti-pruritic (e.g. tricyclic antidepressants, sedatives, tranquilizers, gabapentin, marijuana or other cannabinoids, opioid receptor agonists/antagonists) or pruritic (e.g. opioids, angiotensin-converting enzyme inhibitors, cocaine, antimalarials) properties within 4 weeks prior to randomization.
 - a. Stable doses of H1 antihistamines will be permitted. Subjects must be willing to continue these at the same doses and frequencies throughout the study inclusive of the follow-up period.
- 6. Any clinically significant changes in type, dose, or frequency of bland emollients, low- or mid-potency corticosteroids, and/or oral H1 antihistamines throughout the study from screening to follow-up.
- 7. Treatment with systemic immunosuppressive/ immunomodulatory therapies within 4 weeks prior to randomization (including but not limited to phosphodiesterase-4 inhibitors, cyclosporine, mycophenolate-mofetil, methotrexate, azathioprine, interferongamma, or phototherapy).
- 8. Treatment with biologic therapies within 12 weeks or 5 half-lives prior to randomization, whichever is longer.
- 9. Use of an indoor tanning facility within 4 weeks prior to randomization.
- 10. Treatment with any investigational therapy within 4 weeks prior to randomization.
- 11. Allergen immunotherapy within 6 months prior to randomization.
- 12. Prior use of AO+ Mist.
- 13. History of malignancy within 5 years prior to randomization, with the exception of completely treated and non-metastatic basal cell carcinoma or squamous cell carcinoma of the skin.
- 14. History of a major psychiatric condition (including major depressive disorder, bipolar disorder, or schizophrenia), suicidal ideation, or suicide attempt.
- 15. Known active hepatitis infection.
- 16. Known history of human immunodeficiency virus (HIV) infection.

- 17. Presence of any medical condition or disability that, in the investigator's opinion, could interfere with the assessment of safety or efficacy in this trial or compromise the safety of the subject.
- 18. Currently pregnant or breastfeeding, or male subject with a pregnant or breastfeeding partner.
- 19. Females of childbearing potential who are unable or unwilling to practice highly effective contraception (pregnancy prevention); fertile males who are unable or unwilling to use condoms with female partners of childbearing potential.

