7.5.1 Use of Bland Emollients During the Study

Subjects will be allowed to use their usual choice of bland emollients (e.g., lotion, moisturizer) from screening to follow-up, on an as needed basis, using specific time of use guidelines in relation to study medication application. Subjects will be allowed to use their emollient of choice at a similar dose and frequency throughout the study if used. Any clinically significant changes in type, dose, or frequency of bland emollients will not be allowed during the study. A detailed guideline will be shared with the sites and subjects to ensure consistency in study medication treatment application and relation to body washing, emollient use, and other chemical exposure to skin.

Subjects will be encouraged not to use sunscreen on the treated lesions during participation in the study. Sunscreen should be used minimally or used sparingly while in the active treatment phase (Baseline to Week 4) of the study. Alternatively, sunscreen should be washed off prior to study medication use.

Subjects who do not have atopic dermatitis on their face may apply makeup as needed. However, those subjects who have atopic dermatitis on their face and require to use makeup will be advised to use it minimally.

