8.9 Study Drug Discontinuation

Subjects will be discontinued from study drug treatment in the following events:

- The subject experiences a Grade 2 or higher treatment emergent AE that is assessed as likely related to study drug
- The subject receives treatment with an excluded therapy or has a clinically significant change in dose or frequency of allowed adjunctive therapies during the treatment period
- The female subject becomes pregnant or female partner of a male subject becomes pregnant or is breastfeeding

Discontinuation from study drug treatment may also occur for any of the following reasons:

- Subject decision to discontinue study drug treatment, or subject decision to withdraw consent from the study
- Any medical condition that may jeopardize the subject's safety if study drug is continued, in the investigator's and/or Sponsor's opinion
- Discontinuation is deemed to be in the best interest of the subject, in the investigator's and/or Sponsor's opinion

Subjects who discontinue treatment with study drug prior to completing the treatment period will have an ETD visit within 7 days after their last dose of study drug in addition to a follow-up visit

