11.2.4 Investigator Global Assessment Score (IGA)

IGA will be performed at the times indicated (Screening, Baseline, Day 14, Day 28, and Day 56) in the Time and Events Table of the Protocol (Appendix A) as static IGA. The Investigator will assess improvement of Atopic Dermatitis based on the 5-point severity scale summarized below and in Appendix E.

Score	Category	Definition
0	Clear	Minor residual discoloration, no erythema or induration/papulation, no oozing/crusting
1	Almost Clear	Trace faint pink erythema with almost no induration/papulation and no oozing/crusting
2	Mild disease	Faint pink erythema with mild induration/papulation and no oozing/crusting
3	Moderate disease	Pink-red erythema with moderate induration/papulation and there may be some oozing/crusting
4	Severe disease	Deep/bright red erythema with severe induration/papulation with oozing/crusting

11.2.5 5-D Pruritus Scale

The 5-D Pruritus Scale is a validated, multi-dimensional measure of itching that assesses the five domains of degree, duration, direction, disability and distribution (Appendix F). Subjects rate their symptoms over the preceding 2-week period on a 1 to 5 scale, with 5 being the most affected. Subjects will complete the 5-D Pruritus Scale during study visits as outlined in Appendix A.

11.3 eDiary and Efficacy Assessments

All patient reported outcomes and clinical outcome assessments (ePRO/eCOA) will be obtained electronically using either a smartphone application or a tablet. Participants will be provided with eDiary at screening to initiate daily diary entries from screening to follow-up and will include responses to WI-NRS, AI-NRS, daily dose confirmation (during the treatment period),

rescue medication (if any), and local skin tolerability (Day 1 to Day 7 of treatment). In addition, participants' usual adjunctive therapies (e.g., bland emollient, oral H-1 antihistamine) may be collected using eDiary or CRF at screening and optionally throughout the study. POEM and 5-D Pruritus Scale will be reported by the participants at the designated site visits using a site provided tablet. IGA and EASI will also be assessed at the designated site visits by the clinician.

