PP population excludes subjects with any major protocol deviation that may impact efficacy and safety analyses, including those with any confounding events or those over the rescue medication use limits but includes data for subjects below rescue medication use limits. Rescue medication

STATISTICAL ANALYSIS PLAN

Version 3.0 12-Jan-22

use below the allowed limit per protocol are considered minor protocol deviations, are considered non-confounding, and is included in the PP population.

The following events are confounding:

- Change in stable use of oral H1 antihistamines (e.g., change in type, dose, and frequency of medication)
- Change in stable use of bland emollients (e.g., change in type, dose, and frequency of treatment)
- Use of excluded medications during study
- Use of rescue medications over the allowed limit per protocol (over 3 rescue medication days during the 2-week washout period, over 7 rescue medication days during the 4-week treatment, and over 7 rescue medication days during the 4-week follow-up)

In the PP sub-analysis, all subject data over the rescue medication limits per the PP primary analysis will be excluded, but subject data below the rescue medication limits will be included up to the date or week that the first rescue medication is taken.

Hypothesis tests for the primary efficacy endpoint will be performed using a Dunnett Testing Method, applying pairwise comparisons of each respective B244 dose group to vehicle using a one-sided familywise error rate of 0.10. Section 7.4.2 provides further details. No additional adjustments will be made for multiple testing. As such, p-values from analysis of secondary and exploratory efficacy analyses must be interpreted in an exploratory fashion.

Supportive analyses may be performed for all efficacy analyses combining the B244 dose groups in comparison against vehicle and comparison of the B244 groups to one another.

Furthermore, stratified analyses will be performed by presenting descriptive statistics by age group, race, gender, IGA at Baseline (2 or 3), EASI at baseline (≤ 10 or >10), BSA range at Baseline (10 to 20%, >20 to 30%, >30 to 40%), rescue treatment used at Baseline (Yes, No), and rescue medication used while on treatment (Yes/No).

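### Exclusion 6 runs past randomisation, and the SAP's per-protocol rule lets events after the Week 4 endpoint remove subjects from the Week 4 per-protocol analysis

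*Protocol*

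**What the plan says.** **Eligibility.** Protocol 6.3 opens its list with "Participants will be excluded from the study if any of the following criteria are met". Item 6 of that list is "Any clinically significant changes in type, dose, or frequency of bland emollients, low- or mid-potency corticosteroids, and/or oral H1 antihistamines throughout the study", and its closing words give the span: "oral H1 antihistamines throughout the study from screening to follow-up". The Synopsis and SAP 4.1.1.2 repeat it. Protocol 7.2 requires that no exclusion criterion be met for a subject to be enrolled and randomised.

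**Emollients during the study.** Protocol 7.5.1 allows the subject's usual emollient "from screening to follow-up, on an as needed basis". The same paragraph asks for similar dose and frequency and forbids clinically significant changes, without a threshold. For the treatment period, Protocol 8.9 makes it a reason to stop study drug if the subject "has a clinically significant change in dose or frequency of allowed adjunctive therapies during the treatment period".

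**PP membership.** SAP 7.4 states that the PP population excludes subjects with major deviations, including those with any confounding event. Its list of such events includes "Change in stable use of bland emollients (e.g., change in type, dose, and frequency of treatment)", a parallel item for oral H1 antihistamines, use of excluded medication during the study, and rescue use above the limits, one of which is "over 7 rescue medication days during the 4-week follow-up". SAP 7.2.5 and 7.3.2 are narrower. They speak of major deviations that may affect the efficacy assessments, with removal at the sponsor's discretion after a review before unblinding.

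**Role and timing.** SAP 7.2.6 makes mITT definitive and PP supportive. SAP 6.5.3 ends the Week 4 average at Day 28 or the day before Visit 4, whichever is earlier. SAP 7.5.4 starts follow-up on the day of Visit 4.

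**The concern.** An exclusion criterion has to be decidable when the subject is randomised. The part of exclusion 6 that lies after Day 0 is not, and Protocol 8.9 already provides a separate rule for part of that period. As written, one clause is both an entry criterion and a conduct rule.

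The PP rule has the more direct statistical consequence. A per-protocol set should be defined by adherence up to the endpoint. Here a subject who complied through Week 4 and then needed more than 7 rescue days in follow-up, or changed antihistamine in Week 7, leaves the Week 4 analysis as well. Rescue and emollient use plausibly track itch, so membership then depends on a post-randomisation variable related to the outcome. The PP comparison loses the protection of randomisation for a reason that has nothing to do with adherence during treatment.

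**Working it through.** **Step 1. Timing, from the text alone.**

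| Item | Latest time it can occur | Source |
|---|---|---|
| Eligibility decision | Baseline, before randomisation | Protocol 7.2; Appendix A has the criteria checked only at Screening and Baseline |
| Exclusion 6 | End of follow-up | Protocol 6.3; SAP 4.1.1.2 |
| Week 4 itch average | Day before Visit 4 | SAP 6.5.3 |
| Rescue overuse in follow-up | Visit 4 to the day before Visit 5 | SAP 7.4, 7.5.4; threshold repeated in Listing 16.2.13.3 |
| Emollient or antihistamine change | No limit stated | SAP 7.4 |

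The last two rows extend beyond the third. They still decide who enters Table 14.2.2.2, the PP Week 4 ANCOVA. This needs no assumption about how subjects behave. It also goes beyond SAP 7.2.5, because an event after the Week 4 window cannot affect the Week 4 assessment.

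**Step 2. Wording of the emollient item.** Protocol 6.3, 7.5.1 and 8.9 all restrict the rule to clinically significant changes. The SAP 7.4 emollient item drops that qualifier. Read literally, any confounding event excludes the subject; SAP 7.3.2 says a major deviation may lead to removal. The two cannot both be the operating rule.

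**Step 3. Possible size if removal follows response.** The plan gives no figure to reproduce here. From Protocol 12.1: SD σ = 2.5 and true difference 0.65. Assumed: change scores are normal; mean vehicle change μ is -1.5, -2.0 or -2.5, with B244 lower by 0.65; and a share p of subjects with change ≤ -4 leaves the PP set.

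With a = (-4 - μ)/σ, the share removed is pΦ(a). The retained mean is μ + s, where s = pσφ(a) / (1 - pΦ(a)). The PP difference is 0.65 + s(vehicle) - s(B244).

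Example, μ = -2.0 and p = 0.50:
- Vehicle: a = -0.80, φ = 0.2897, Φ = 0.2119. So s = 0.5 × 2.5 × 0.2897 / (1 - 0.1059) = 0.405.
- B244: μ = -2.65, a = -0.54, φ = 0.3448, Φ = 0.2946. So s = 1.25 × 0.3448 / (1 - 0.1473) = 0.505.
- PP difference = 0.65 + 0.405 - 0.505 = 0.55.

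| p | PP difference, μ = -1.5 / -2.0 / -2.5 | Removed, B244 | Removed, vehicle |
|---|---|---|---|
| 0.25 | 0.61 / 0.61 / 0.61 | 5.7% / 7.4% / 9.2% | 4.0% / 5.3% / 6.9% |
| 0.50 | 0.55 / 0.55 / 0.56 | 11.5% / 14.7% / 18.3% | 7.9% / 10.6% / 13.7% |

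The loss is about 0.04 at p = 0.25 and 0.09 to 0.10 at p = 0.50.

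Removal can also come from the other end. In a simulation with μ = -2, removing 50% of subjects with no improvement (change ≥ 0) gives 0.55, and removing 50% at both ends gives 0.46.

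**Step 4. Under the null.** If the arms share one distribution and removal depends only on the subject's own change, s is equal in both arms and the PP difference is 0. The simulation agrees.

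**The case against.** The strongest reply is that little rests on this. The mITT analysis is definitive and drops nobody for adjunctive or rescue use. A reader might take PP to be the only planned support for it, but SAP 7.4 also specifies, within mITT, a four-diary sensitivity analysis, a sub-analysis excluding data after rescue, and non-responder imputation. The addendum adds worst-observation and all-randomised last-observation analyses. That part of the reply stands and sets the weight of the point.

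Three further stronger readings are tempting and not supported.

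- **That exclusion 6 contradicts Protocol 7.5.1.** The as-needed phrase sits beside the same limit on clinically significant changes. What is missing is a threshold.
- **That adjunctive use is collected only optionally.** Protocol 11.3 says it "may be collected using eDiary or CRF at screening and optionally throughout the study". However, Protocol 8.13 requires any medication, including over-the-counter products, to be recorded with dose and frequency through the final visit, and Appendix A schedules that review at every clinic visit. The two sections need aligning; the data are not simply absent.
- **That everyone whose emollient frequency drifts will be removed.** SAP 7.4 speaks of change in stable use, and SAP 7.3.2 grades deviations under separate guidance, with discretion before unblinding. SAP 7.4 gives no direction of change, so whether a reduction would count is an inference.

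It is also fair that eligibility is checked only at Screening and Baseline, so listing a correctly entered subject as an entry violation is a risk of the wording rather than a planned step.

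Blinded review does not answer the timing fault. A blinded reviewer who applies the follow-up threshold as written removes subjects on events after the endpoint.

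**Conclusion.** The point holds in limited form. On the text alone, exclusion 6 contains a part that cannot be judged at randomisation, and SAP 7.4 lets events after the Week 4 window decide membership of the Week 4 PP analysis. The missing qualifier and the tension between SAP 7.4 and SAP 7.2.5 and 7.3.2 leave the emollient rule open to more than one application.

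The consequence is confined to supportive analyses. If removal follows response, the PP difference shrinks, to about 0.61 to 0.55 from 0.65 in the illustration with improvers removed. Those removal rates and the vehicle means are assumptions; the documents give neither. A reader might infer a risk of a false-positive PP result. Under response-only removal there is none. Bias in either direction would need treatment to alter adjunctive use by a route other than itch, and the documents offer no evidence on that. The changes are worth making because they cost little, not because the trial's main conclusion depends on them.

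**What to change.** 1. **Exclusion 6** (Synopsis, Protocol 6.3, SAP 4.1.1.2): limit it to changes from Screening to Baseline, checked before randomisation. Record later changes as protocol deviations.
2. **SAP 7.4, timing**: let a confounding event or rescue overuse remove a subject from Week 4 PP analyses only if it occurs before Visit 4. Follow-up events should affect only the Week 5 to 8 PP analyses.
3. **SAP 7.4, wording**: carry over the protocol's clinical-significance qualifier, and reconcile the any-event exclusion with the major-deviation and discretion language in SAP 7.2.5 and 7.3.2.
4. **Reconciliation by the sponsor**: Protocol 7.5.1, 8.9, 8.13 and 11.3 should describe the same event, and its capture, consistently. Which care rule stands is for the sponsor.

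The cost is protocol and SAP wording, with no new data collection. The downside is that the Week 4 PP set keeps some subjects whose adjunctive or rescue use changed after Week 4.
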